4.1.1 Primary Endpoint

The primary efficacy endpoint is SVR₁₂ (HCV RNA <LLOQ 12 weeks after cessation of therapy).

The primary statistical hypothesis for efficacy is that SVR_{12} rate is higher than the conservative estimate of $70\%^{20}$.

- $H_0: SVR12 = 70\%$
- $H_a: SVR12 \neq 70\%$

The primary analysis will be intention-to-treat, including all enrolled subjects into the study and received at least one dose of study drug, performed after all enrolled subjects have been followed through 12 weeks post-treatment or discontinued from study.

4.1.2 Secondary Endpoints

Secondary efficacy endpoints include: HCV RNA < LLOQ at 4 and 24 weeks after discontinuation of therapy (SVR₄ and SVR₂₄); viral breakthrough; and relapse.

Descriptive summaries and listings will be provided for additional efficacy evaluations of the proportion of subjects who experience virologic failure and other endpoints of interest including ALT normalization, serum HCV RNA actual values, and change from baseline.

Exploratory analyses may be performed to assess the relationship between demographic, baseline characteristics, (including baseline viral load, genotype, age, sex, race, ethnicity, presence/absence of cirrhosis, baseline ALT level, prior treatment experience, response to previous treatment [if applicable], and BMI) and antiviral activity (HCV RNA reduction, proportion of subjects with HCV RNA <LLOQ at various time points during and following discontinuation of all therapy). Predictive factors of antiviral activities may be examined using regression type of analysis. Changes in HCV specific CD8 responses in patients with cirrhosis and not with cirrhosis. Changes in HCV specific immune responses in patients treated with single (NS5B) DAA versus dual (NS5B + NS5A) versus triple combination DAA (NS5B + NS5A + NS3) using samples from SPARE and this study

4.1.3 Safety Endpoints

The primary safety endpoint is any AE leading to permanent discontinuation of study drug(s).

4.1.3.1 Other Endpoints of Interest

Additional efficacy evaluations may include HCV RNA change from Day 0; ALT normalization; and viral kinetic parameters.

4.1.4 Analysis Sets

4.1.4.1 Efficacy

The analysis set for antiviral activity analyses will include subjects who were enrolled into the study and received at least one dose of study drug.

4.1.4.2 Safety

The primary analysis set for safety analyses will include subjects who received at least one dose of study drug.

Safety will be evaluated by assessment of clinical laboratory tests, physical examinations, and vital signs measurements at various time points during the study, as well as the documentation of AEs.

On treatment data will be analyzed and defined as data collected from the first dose of study drug through the date of last dose of study drug plus 30 days.

4.1.4.3 Pharmacokinetics

The PK analysis set will include all subjects who are enrolled and have received at least one dose of study medication. The PK analysis set will be used for analyses of general PK. The intensive PK analysis will include the 20 participants who were enrolled in the sub study.

4.2 DATA HANDLING CONVENTIONS

Missing data can have an impact upon the interpretation of the trial data. Other than the endpoints discussed below, values for missing data will not be imputed.

For the analysis of post-baseline categorical efficacy endpoints, if a data point is missing and is preceded and followed in time by values that are deemed successes, then the missing data point will be termed a success; otherwise the data point will be termed a failure.

Any subject with missing data due to premature discontinuation of the study medication will be considered a failure at the time points on, or following, the date of discontinuation. If no HCV RNA values are obtained after the last dose of study medication, the subject will be considered a treatment failure for the SVR endpoints.

Where appropriate, safety data for subjects that did not complete the study will be included in summary statistics. For example,

- If a subject received study medication, the subject will be included in a summary of adverse events according to the treatment received; otherwise, if the subject is not dosed then they will be excluded from the summary.
- If safety laboratory results for a subject are missing for any reason at a time point, the subject will be excluded from the calculation of summary statistics for that time point. If the subject is missing a pre-dose value, then the subject will be excluded from the calculation of summary statistics for the pre-dose value and the change from pre-dose values.

Values for missing vital signs data will not be imputed; however, a missing Day 0 result will be replaced with a screening result, if available.

4.3 DEMOGRAPHIC DATA AND BASELINE CHARACTERISTICS

Demographic and baseline characteristics will be summarized using standard descriptive methods by treatment arm and overall.

Demographic data will include sex, self-identified race/ethnicity, and age.

Baseline characteristic data will include body mass index (BMI), presence or absence of cirrhosis, HCV RNA level (log₁₀ IU/mL), HCV genotype, and additional endpoints as necessary.

4.4 ADVERSE EVENTS

Events will be summarized on the basis of the date of onset for the event. A treatment-emergent adverse event will be defined as any new or worsening adverse event that begins on or after the date of first dose of study drug up to the date of last dose of study drug plus 30 days.

Summaries (number and percentage of subjects) of treatment-emergent adverse events will be provided.

5 STUDY TESTS

5.1 SCHEDULE OF TESTS

Laboratory Studies

Screening tests that have been done as part of other studies or standard of care within the last 8 weeks or at an outside facility (with the exception of safety labs chemistries, hCG, CBC with differential, coagulation studies) can be used if within the 8 weeks prior to Day 0. HIV test does not need to be done in participants known to be HIV infected. Similarly, HBV serologic testing does not need to be done in participants known to be chronically HBV infected who are on suppressive therapy.

Serum Chemistry and Hematologic Profiles

Acute Care Panel, Hepatic Panel, Mineral Panel, and CBCs (with differential) will be performed to monitor clinical status, document drug-related benefits and detect potential drug-related toxicities. These may be done on screening, days 0, 7, 14, and every scheduled visit thereafter through post-treatment Week 24. Highly sensitive C-reactive protein may also be done at Days 0, weeks 1 (optional), 2, 4, 12 (end of therapy), as well as post-treatment weeks 12 and 24, again dependent upon blood volume availability by patient.

Prothrombin Time and Partial Thromboplastin Time

Measured by standard assay on screening, end of therapy (Week 12), prior to liver biopsy and post-treatment Week 24.

Creatine Kinase, Lactate Dehydrogenase, Lipase, Amylase.

Measured by standard assay on screening and Weeks 4, end of therapy (Week 12) and post-treatment Week 12.

Alpha Fetoprotein, HCV genotype, Hemoglobin A1C, HIV testing.

Measured by standard assays as part of screening. Hemoglobin A1C will be repeated at Day 0, End of therapy: (Weeks 12), and post-treatment Weeks 12 and 24.

Serum/Urine Pregnancy Test

Measured by standard assay on screening, on Day 0, and then every 4 weeks while on treatment and at every visit post treatment completion for women of childbearing potential.

SOF/VEL/VOX level

Measured at scheduled study visit continuing through the End of Treatment visit. Actual date and time of PK sample collection and study drug administration will be recorded.

HCV RNA Levels (HCV Viral Loads)

This will be performed at the following study points: screening; day 0; weeks 1 (optional visit), 2, 4, 8; end of therapy (week 12); post treatment weeks 4, 12, and 24.

HCV Genotype Assay

This will be performed at screening if not on file. A result from an outside lab can be used if it was completed after documented treatment failure.

HIV RNA Test

This will be performed in HIV coinfected individuals at the following study points: screening, day 0, weeks 4, 8, 12 and post-treatment week 12.

CD4 Test

This will be performed in HIV coinfected individuals at the following study points: screening, week 12 and post-treatment week 12.

HBV DNA Test

This will be performed in chronically HBV-infected individuals at the following study points: day 0, on-treatment weeks 4, 8, and 12 and post-treatment weeks 4 and 12.

VK/PK Sub Study

Subjects will have blood drawn at time points 0, 1, 2, 4, 8, 24 and 72 hours after administration of drug to assess drug levels and HCV viral load levels.

Research tests

HCV Virologic Studies

Full length HCV genome pyro sequencing may be performed using the protocol as described and compared for variability of sequences²⁷.

DNA Methylation Studies

Promoter methylation status for candidate genes or at a whole genome level using methylation–specific PCR may be performed on tissue samples²⁸.

rs12979860 (IL28B) Genetic Variant

IL28B genetic variants have been shown to predict HCV treatment induced clearance²⁹. The IL28B assay is a real-time PCR assay that utilizes 5-prime nuclease activity of a thermostable polymerase and unique primers and SNP-specific probes to determine the genotype. Test results will not be used as inclusion or exclusion criteria.

Immune Responses to HCV

Both humoral and cellular immunity against HCV will be estimated before and during treatment to assess the effect of HCV treatment on host immune response against HCV. We may also perform multiplex PCR assays to detect ISGs before and during treatment.

HCV Genotypic and Phenotypic Resistance Monitoring

Serum samples for genotypic and phenotypic monitoring will be collected. Resistance monitoring will be completed in all subjects who received study drug and where virologic failures as defined.

Subjects who are determined by sequencing and phenotypic analysis to have had mutations leading to SOF resistance will be requested to return at 12 week intervals for up to 48 weeks after the last dose of study drug to determine the time for the resistant virus to return to background levels.

Immunophenotyping for T cells

We will study the effectiveness of DAA therapy for normalizing effector T and B cell populations. Peripheral or hepatic lymphocytes will be evaluated using flow cytometry for different activation and exhaustion markers. Lymphocytes will be stained with conjugated-antibodies against CD3, CD4, CD8, CD56, CD45RA, CCR7, CD69, CD25, HLA-DR, CD38, Ki67, FoxP3, CTLA4, Tim-3, PD-1 and CD57. The percentage of cells expressing each and multiple markers will be determined by flow cytometry (BD FACSAria). Data will be analyzed using FlowJo (TreeStar) software.

Determination of HCV specific polyfunctional CD4 and CD8 T cells

For characterization of HCV specific T cell phenotype and function, peripheral T cells will be isolated from PBMCs by Ficoll-paque density gradient separation to be stimulated with pooled HCV genotype specific peptides. For this experiment, we will use HCV 15-18-mer peptides with 11 or 12 amino acid overlaps spanning the entire HCV polyprotein (Mimotopes, Peptide Array, HCV), reconstituted in 5% sterile dimethylsulphoxide (DMSO), pooled consecutively into twenty-one groups and aliquotted until use. The number of HCV-responsive IFN- γ -producing PBMC will be quantified by standard ELISPOT assay (BD Biosciences), in which 96 well ELISPOT plates are coated with anti-IFN- γ biotinylated capture antibody and incubated overnight at 4°C. Plates will be blocked using lymphocyte medium, and PBMC allowed to rest for 6 hours at 37°C. PBMC will be plated between 250,000- 400,000 cells per well with either phytohaemagglutinin (PHA) as a positive control (5 mg/ml), DMSO as a negative control (0.05%), or pooled HCV peptides (3 mg/ml/peptide). All cultures will be performed in duplicate. After incubating for 12 hours at 37°C, cells will be removed, and plated with streptavidin detection antibody, enzyme conjugate, and substrate. The plates will then be air dried in the dark overnight, and developed spots will be enumerated using an ELISPOT plate reader.

Further testing of HCV responsive T cells will be conducted by flow cytometric analysis. To identify HCV responsive cell populations, carboxyfluoresceinsuccinimidyl ester (CFSE) dilution will be utilized. PBMC will be washed and incubated with 2.5mM CFSE (Invitrogen) at 37°C for 6 minutes, guenched with PBS + 5% fetal calf serum (FCS), and washed three times with lymphocyte medium. PBMC will be incubated at 5×10^6 in 1.2 mL with either pools of overlapping HCV peptides spanning the entire proteome (3mg/mL/peptide) or DMSO (1%) and NH₄OH (0.7mM) as a vehicle control for a total of 48 hours. Brefeldin A and monensin will be added at 36 hours to block the Golgi apparatus and allow intracellular cytokine accumulation. Following incubation, PBMC will be harvested and stained with LIVE/DEAD Near-IR (Invitrogen) for 30 minutes on ice. The percentage of live, CFSE+ cells will be assessed by flow cytometry data (FACSAria) and analyzed using FlowJo software (TreeStar) for phenotype and function using the antibodies described previously. To assess secreted cytokine production, 100 ul of supernatant will be collected at 36 hours and frozen at -80°C until used. Samples will be thawed and analyzed for cytokine production using Mesoscale Discovery Human TH1/TH2 10plex ultra-sensitive kit (catalog #K15010C-1) according to manufacturer's protocol. All samples will be tested in duplicate.

Determination of T cell defects in liver with mass cytometry using CYTOF

Liver infiltrating lymphocytes (LIL) will be isolated from liver biopsy specimen and evaluated for markers of immune exhaustion and activation on effector and memory T cell subsets. Because we are able to obtain limiting number of lymphocytes from liver biopsies (up to 1 million cells per biopsy) it will be critical to use a technology that maximize the spectrum of T cell phenotypes visualized. Although flow cytomtery-based immunophenotyping has been extensively used to connect polyfunctionality and memory phenotypes of T cells, it is limited by its inability to discern all distinct cellular phenotypes and relate them to one another without the ability to evaluate simultaneously at many phenotypic markers, functional capacity, and antigen specificity in individual cells. Flow cytometry is limited by its ability to evaluate 12-18 parameters because of overlapping excitation and emission spectra between different fluorophores. We plan to use a recently developed single-cell mass spectrometric (cytometry by time-of-flight or CyTOF) approach in which heavy metal isotopes are used to label antibodies and then labeled cells are analyzed by high throughput mass spectrometry to quantify 34 parameters at the single-cell level, with very little crosstalk between channels. This approach will allow us to evaluate more than 30 functional phenotypes represented by distinct CD8+ T cell subsets, a nearly combinatorial diversity in the critical liver infiltrating lymphocyte population. Phenotypic and functional characterization of liver cells will be done on 10 subjects with no liver fibrosis and compared with 10 advanced stage liver fibrosis subjects using mass cytometry analysis. We will test the samples for levels and exhaustion status of their HCV specific polyfunctional T cells. The University of Maryland School of Medicine Cellular Flow Cytometry Core Lab will provide technical assistance in design, data acquisition and analysis of all CyTOF experiments on fee-for-service basis.

Flow cytometry for B cell phenotyping

B cell subpopulations will be phenotyped by flow cytometry at baseline (pre-treatment) and at the end of treatment and compared with samples from healthy volunteers as controls, matched for age and gender. Multicolor flow cytometry analyses will be performed on cryopreserved PBMC. Lymphocyte counts will be determined by a core facility following standard procedures. The frequency of each B cell subpopulation will be determined by flow cytometry. The following fluorochrome-conjugated monoclonal antibodies will be used in the B cell staining strategy: V450 anti-CD3 (BD Biosciences, Carlsabad, CA); PerCP-Cy5.5anti-CD19, PE-Cy7 anti-CD27 (eBioscience, San Diego, CA); FITC anti-CD21 (Beckman Coulter, Brea, CA);allophycocyanin (APC) anti-CD10, APC-H7 anti-CD20 (BD Biosciences, San Jose, CA); PE anti-CD95 (BD Biosciences, Carlsabad, CA). Analyses will be performed on a FACSAria flow cytometer (BD Biosciences, San Jose, CA) with FlowJo software (TreeStar, Ashland, OR). The following B cell subpopulations will be defined: immature/transitional, naïve, resting memory, tissue-like memory, plasmablast, and activated memory.

Determination of antigen specificity of B cells

In previous work, we performed immunophenotyping of B cells, which demonstrated persistence of abnormal phenotype of peripheral B cells in chronic HCV infected subjects undergoing treatment with 3DAAs. In this regard, there was a higher percentage of TLM B cells present in the peripheral blood of patients at the end of antiviral therapy. Using samples stored from patients from previous protocols, we will determine the antibody responses to HCV antigens during and after treatment in this study. Ruc-antigen fusions, including HCV core, have been previously described. We modified the LIPS technology for simultaneously screening protein panels arranged in a 96-well microtiter plate format. For these studies, extracts of Ruc fusions with proteins from HCV, and Influenza were first produced and stored frozen at–80°C to be used to generate an "antigen cell" for each protein. After incubation with serum samples, the serum-Ruc-antigen mixtures from each well of the microtiter plate were transferred to microtiter filter plates containing protein A/G beads. Each 96-well filter plate was then processed in the standard LIPS format for washing and measuring light units (LU) using a plate luminometer. Luciferase immunoprecipitation assays for profiling and quantification of these Ruc-antigens will be performed in duplicate as previously described at baseline, weeks 4, 12 and 24 using 50 uL of cryopreserved serum per assay. Antibody titers, reported in LU, will be reported as the average of two independent experiments, after correction for background LU values. Changes in antibody titer from baseline and absolute antibody titers will be measured in patients undergoing treatment and compared.

RNA Seq Analysis.

We will perform transcriptional analysis of whole blood (Paxgene) and LILs. Illumina RNAseq libraries will be prepared with the TruSeq RNA Sample Prep kit (Illumina). Between first and second strand cDNA synthesis, the primers and nucleotides will be removed from the samples with NucAway spin columns (Ambion). The second strand will be synthesized with a dNTP mix. Adapters containing 6 nucleotide indexes will be ligated to the double-stranded cDNA. After adapter ligation, the second strand cDNA will be digested with 2 units of Uracil-N-Glycosylase (Applied Biosystems). The DNA will be purified between enzymatic reactions and the size selection of the library will be performed with AMPure XT beads (Beckman Coulter Genomics). The quantity and size of the libraries were assessed on the LabChip GX (Perkin Elmer) and with the Library Quantification Kit for Illumina (Kapa Biosciences)³⁰. Analysis of data, including alignment and statistical analysis

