2.3 EXPLORATORY OBJECTIVES

- Characterize immunologic, virologic, and host genetic/proteomic predictors of response
- Viral kinetic investigations, including early viral kinetics, resistance associated variants, HCV quasispecies
- To determine the impact of liver cirrhosis in SVR when treated with potent combination DAA therapy
- To delineate the precise effects of specific HCV lifecycle inhibitors on host immune recovery in patients receiving combination DAA therapy
- To compare the immunophenotypic responses of patients receiving SOF/VEL/VOX who have previously failed double and triple DAA therapy.
- 2.3.1 Rationale for Immunologic studies

We propose to study the B and T cell immune responses most associated with chronic HCV eradication after DAA therapy, in order to more fully understand the utility of new ultra short duration therapies for those chronically infected with HCV. We will define T cell immune responses associated with protective immunity in chronic HCV infection and further advance our understanding about host immunity that is associated with SVR. Studies on

B and T cell responses in HCV or HCV/HIV dual infection and the relationships to treatment outcomes require large numbers of patients and extensive clinical trials of DAA therapy. Our research team is making a major impact on the clinical understanding of DAA. We have collected and maintain a large specimen repository that is sufficient for our initial characterization of B and T cells and how they are related to protective immunity.

Chronic HCV infection is characterized by dysfunction of the adaptive immune system. DAA therapy is successful in resolving HCV infection and provides cure in up to 99% cases, except for late stage disease. Whether cure is associated with reconstituted immune regulation and what role the adaptive immune system plays in viral clearance is not known. Faster resolution of secondary infection after spontaneous clearance of HCV in humans and in chimpanzees points to a role for immunological memory in HCV control. Defining the immune correlates of DAA mediated sustained virologic response will help understand the immune defects that may be associated with treatment failure.

Hypothesis

[figure not shown]
Hypothesis #1: Augmentation of HCV specific cellular immune responses with DAA therapy is associated with SVR.

Hypothesis #2: Healthy (non cirrhotic) liver is critical in mounting HCV specific cellular immunity in DAA treated patients

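### The CFSE flow readout is stated as the share of CFSE-positive cells, but the assay identifies responders by CFSE dilution, so the stated quantity does not isolate them

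*Combined protocol and SAP*

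**What the plan says.** The assay is described in section 5.1, under Determination of HCV specific polyfunctional CD4 and CD8 T cells. It follows an ELISPOT count and is presented as further testing of responsive T cells.

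- Identification rule: "To identify HCV responsive cell populations, carboxyfluoresceinsuccinimidyl ester (CFSE) dilution will be utilized".
- Labelling comes before stimulation and covers all the cells: "PBMC will be washed and incubated with 2.5mM CFSE (Invitrogen) at 37°C for 6 minutes". (The concentration unit may be an artefact of text extraction, and nothing here depends on it.)
- The labelled cells are cultured with overlapping HCV peptides or with DMSO and NH4OH "as a vehicle control for a total of 48 hours".
- Readout, after a viability stain: "The percentage of live, CFSE+ cells will be assessed by flow cytometry data (FACSAria". The same sentence goes on to say that the data are "analyzed using FlowJo software (TreeStar) for phenotype and function using the antibodies described previously".

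Neither this paragraph nor any other part of the document gives a CFSE-low or divided-cell gate, a division or proliferation index, or a rule for using the vehicle well in this readout.

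The aims in this area are secondary endpoint 8 in the Study Summary, repeated in section 4.1.2 ("Changes in HCV specific CD8 responses in patients with cirrhosis and not with cirrhosis"), and Hypothesis 1 in section 2.3.1 ("Augmentation of HCV specific cellular immune responses with DAA therapy is associated with SVR").

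**The concern.** In a dye-dilution assay every cell starts positive, and a cell that responds by dividing passes half its dye to each daughter. The information is in the loss of dye, not its presence. The paragraph names the right principle and then states a quantity that does not use it. The population named in that quantity is also the one carried forward to phenotype and function.

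A laboratory that followed the sentence literally would report either a near-constant or a number that moves against the response. Its phenotype and function results would describe mainly cells that had not divided. Direction matters because Hypothesis 1 is about augmentation of the response. Leaving the gate unstated also leaves a choice open until after the data have been seen.

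**Working it through.** The plan gives no expected value, sample size or power for this readout, so there is no stated figure to reproduce. The check is a count of cells and dye.

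**Inputs from the plan (section 5.1):** all PBMC labelled before culture; 48-hour culture; responders identified by dilution; readout based on live CFSE-positive cells.

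**Assumed inputs (not in the documents):** a share p of starting cells responds, with p = 0.1%, 1% or 3%; each responder divides g = 1 or 2 times; the other cells do not divide; the starting label is well above background.

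**Formulas.** Responders yield p·2^g daughters, each holding 1/2^g of the starting dye. The remaining 1 − p cells keep all of theirs.

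- CFSE-low share = p·2^g / (1 − p + p·2^g)
- Undivided share = (1 − p) / (1 − p + p·2^g)

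**Worked case, p = 1%.**

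- g = 1: CFSE-low = 0.02/1.01 = 1.98%; undivided = 0.99/1.01 = 98.02%.
- g = 2: CFSE-low = 0.04/1.03 = 3.88%; undivided = 0.99/1.03 = 96.12%.

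**Range.**

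| p | g | CFSE-low (what dilution identifies) | CFSE+ read as dye-bright | CFSE+ read as any dye |
|---|---|---|---|---|
| 0.1% | 1 | 0.2% | 99.8% | about 100% |
| 0.1% | 2 | 0.4% | 99.6% | about 100% |
| 1% | 1 | 2.0% | 98.0% | about 100% |
| 1% | 2 | 3.9% | 96.1% | about 100% |
| 3% | 1 | 5.8% | 94.2% | about 100% |
| 3% | 2 | 11.0% | 89.0% | about 100% |

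**Reading 1, any dye above background.** Divided cells still hold 50% of the dye after one division and 25% after two, so they stay positive. The readout does not move with the response. At p = 1%, 98.0–96.1% of the cells passed to phenotyping are undivided.

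**Reading 2, dye-bright.** The readout is the complement of the CFSE-low share. It falls as the response rises, and every cell passed to phenotyping is undivided.

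The sizes depend on p and g. The direction does not, as long as some responders divide within the culture.

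**The case against.** The best defence is that the governing sentence already says dilution. On that view the disputed phrase, which follows the viability stain, only names a parent gate of viable, labelled cells. A laboratory running this assay would hardly report dye-bright cells as responders. The antibodies listed earlier in section 5.1 include Ki67 and the activation markers CD69, CD25, HLA-DR and CD38, so dividing or activated cells could be picked out within a broad gate.

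That reading is possible, but the text does not carry it. No second gate follows, and no rule uses Ki67 or the activation markers to define HCV-responsive cells. Brefeldin A and monensin are added, which suggests intracellular cytokine staining, yet the flow panel listed under Immunophenotyping for T cells contains no cytokine antibody.

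Other parts of the defence stand, and they rule out stronger conclusions that a reader might draw:

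- *That the plan's HCV-specific T-cell measurement as a whole is wrong.* It is not. ELISPOT is a separate count ("The number of HCV-responsive IFN- γ -producing PBMC will be quantified by standard ELISPOT assay"), and supernatant cytokines and the liver CyTOF work are also separate.
- *That secondary endpoint 8 or Hypotheses 1 and 2 would come out null or reversed.* No section makes this percentage the measure for any of them, and section 4.1.2 places the CD8 item in a paragraph of exploratory analyses that may be done.
- *That the missing vehicle subtraction is itself an error.* The vehicle well is run. Section 5.1 states a background correction for the antibody (LIPS) assay but gives no subtraction formula for ELISPOT either. Subtraction here is a secondary preference.
- *That the percentages above estimate bias in a planned comparison.* They rest on assumed inputs and only show how the two gates behave.

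**Conclusion.** The stated readout is wrong as written. It conflicts with the identification rule in its own paragraph, and under either literal meaning of CFSE-positive it does not isolate the responding cells. With an assumed 1% precursor frequency and one to two divisions, the quantity of interest is 2.0–3.9%, while the written one is 98.0–96.1% or about 100%.

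The point is minor. It concerns one research immunology readout among several. SVR12, the safety endpoints and the sample size do not depend on it. Gates are set in software after acquisition, so recorded events can be re-gated if the files are kept. The documents do not show that the laboratory intends to count undivided cells; loose wording for a CFSE-low gate is quite possible, in which case the correction only records what is meant.

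**What to change.** In section 5.1 or the laboratory manual, replace the readout with wording such as: the percentage of live CD3+CD8+ cells, and separately of live CD3+CD4+ cells, that are CFSE-low, with the gate set on the undivided peak of the same sample's vehicle well and the result reported against that well; phenotype and function are analysed within the CFSE-low gate. If subtraction of the vehicle value is preferred to showing the two side by side, say so before analysis.

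The change should not make this value the sole measure for secondary endpoint 8 or for Hypotheses 1 and 2, because the plan does not choose it over ELISPOT or CyTOF.

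The cost is one or two sentences. The labelled cells, vehicle wells and CD3, CD4 and CD8 antibodies are already planned, so no new samples or assays are needed. If the vehicle value is subtracted, results will be lower and slightly noisier.
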